## 1 PROTOCOL SUMMARY

### 1.1 SYNOPSIS

**Title:** Piloting Pathways, a Hope-enhancing Intervention to Address Activity and Role Function in Metastatic Lung Cancer Patients

**Grant Number:** 1R03CA235171-01A1

**Principal Investigator:** [name]  
Assistant Professor, Behavioral Science

**Study Description and Objectives:** This is a Stage I, single-site trial to refine and then test the feasibility and acceptability of a novel intervention, Pathways.

#### Primary Objectives

1. To refine the Pathways intervention and study protocol based on acceptability feedback from an open pilot study (i.e., fully implement the intervention) with patient exit interviews ( $n = 6$ ). We will use feedback on the acceptability of session content, length, and delivery, and review intervention session recordings to refine the intervention. If necessary, we will refine the procedures for enrollment and retention.
2. To determine Pathways intervention feasibility in a single-arm pilot study ( $n = 55$  Pathways). Feasibility will be defined by enrollment ( $\geq 60\%$ ); primary feasibility outcome, retention ( $\geq 70\%$ ), adherence ( $\geq 70\%$  of patients completing 3 of 5 sessions), and mean acceptability ratings (scores of  $\geq 7$  out of 10 on intervention relevance, helpfulness, and convenience).

#### Secondary Objective

1. To assess preliminary data on intermediate and outcome variables and clinical utility in the single-arm pilot of Pathways. We will assess pre (baseline) to post (~8 weeks after baseline) changes in intermediate (e.g., hope) and outcome (primary: activity and role function) variables related to a future efficacy trial.

**Endpoint:** Feasibility, primary endpoint defined as  $\geq 60\%$  eligible and approached patients enrolled

[figure not shown]
**Study Population:** 61 ( $n = 6$ , Phase I;  $n = 55$ , Phase II) patients receiving infusion-based systemic therapy for stage III, IV non-small cell lung cancer, extensive stage small cell lung cancer, 3-12 weeks into tx, ECOG 0-2

**Stage:** Stage I (Pilot – Refining and Feasibility testing)

**Facilities Enrolling:** UK Markey Cancer Center

Description of Study Intervention:	5-session, supportive care intervention designed to coincide roughly with infusion schedules (2 in-person sessions, 3 phone sessions), delivered 1:1, supporting materials (handouts)
Study Duration:	18 months
Participant Duration:	4.5 hours over ~6-8 weeks

## 1.2 SCHEMA

## Schedule of Activities

	Pre-screening (Pre-consent)	Visit 1 day 1 (must be within 21 days of screening)	Visit 2	Visit 3	Visit 4	Visit 5	Visit 6	Visit 7	Day 360
EHR Review Eligibility	X								
Activities involving patient contact									
Patient refusal form		X							
Informed Consent		X							
Baseline (T0) Patient-reported outcome assessment		X							
Post (T2) Patient-reported outcome assessment								X	
Treatment receipt assessment (T1)				X				X	
Treatment expectancy assessment (T1)				X					
Intervention			X	X	X	X	X		
As needed, patient withdrawal, discontinuation form		X	X	X	X	X	X		
Activities involving research staff (No patient contact)									
Fidelity rating			X	X	X	X	X		
Intervention process notes			X	X	X	X	X		
Treatment enactment assessment			X	X	X	X	X		
EHR review for services used, events								X	X

## 2 INTRODUCTION

### 2.1 STUDY RATIONALE

Each year, roughly 130,000 people are diagnosed with advanced stage lung cancer. Despite its high incidence and considerable disease burden, patients with lung cancer are psychosocially underserved, with very few interventions developed to meet their needs and address their concerns. Chief among these concerns for 40-65% of patients is concern about difficulty pursuing activities and roles related to family, social, work, and leisure (i.e., activity and role function). These concerns are associated with significant distress, yet are not a focus of existing lung cancer interventions. Our preliminary work has demonstrated that patients with higher hope, defined as perceiving that one is working towards personal goals, is associated with better function. Hope may be an appropriate intervention target to support function.

Based on patient feedback and preliminary data, we have developed a brief intervention, *Pathways*, to improve activity and role function in patients with metastatic non-small cell lung cancer. We propose to implement *Pathways* and conduct patient interviews to refine materials and procedures (Phase I, n = 6) and test intervention feasibility and acceptability in a single arm trial (Phase II, n = 55). It is critical to establish acceptable materials and feasible procedures before testing efficacy.

**Premise:** Based on theory and preliminary data, increasing patient hope (i.e., patient perception that they are pursuing their goals and have multiple routes to those goals) through an intervention in primary oncology may be a feasible approach to improve activity and role function.

**Impact:** This intervention is inherently patient-centered and designed to overcome utilization barriers. It may be generalized to other advanced cancers and sustained beyond research to improve care

### 2.2 BACKGROUND

**Lung cancer patients represent a large and underserved population in high need of supportive care interventions that overcome utilization barriers.** Lung cancer has the second highest incidence and highest cancer mortality among men and women in the U.S. Each year, 90,000 people are diagnosed with metastatic non-small cell lung cancer (NSCLC). Lung cancer is associated with high physical and psychosocial morbidities, including poorer physical and role function, higher depression, and more unmet supportive care needs compared to other cancers. Lung cancer patients face major barriers (e.g., time constraints, stigma about psychosocial care) to utilizing supportive services, including stigma related to the disease's poor prognosis and association with smoking. Stigma reflects perceived negative appraisal from others, constrained disclosure of diagnosis and concerns, and internalized self-blame, shame, or guilt and is associated with depression and poorer

social, role, and physical function. Despite a clear need, few supportive care interventions have been developed for lung cancer patients.

**Activity and role function concerns are prevalent, distressing, and not addressed by interventions.** Between 40-65% of lung cancer patients report impaired activity and role function (i.e., activities and roles related to family, social, work, and leisure) as an unmet supportive care need. The consequences of these concerns are decreased survival and quality of life, including depression, loss of life purpose, and perceived burden on others. Functional concerns are prominent and distressing to lung cancer patients throughout cancer treatment, yet are under addressed in primary oncology and supportive care interventions for lung cancer, which emphasize symptom or distress management. This is a critical time to develop interventions to address functional concerns; metastatic NSCLC patients are living longer with potentially more tolerable side effects due to immunotherapy. Our work with patients on immunotherapy suggests activity and role function concerns are still common, as are barriers to utilizing supportive care.

**Increasing patient hope is a promising approach to improve activity and role function.**

Patients with metastatic cancer strive to maintain function in valued activities and roles by setting and pursuing personal goals. Patient hope, a motivational state that reflects goal-directed determination (i.e., agency) and planning to meet goals (i.e., pathways), directly supports goal setting and pursuit. People with higher hope set more goals and ways to reach them and better attain goals. Our work suggests increasing hope may improve activity and role function in lung cancer patients, even in the presence of likely goal obstacles such as symptom burden and stigma. Our work also shows higher hope is related to better function, less depression, and less stigma in metastatic NSCLC (Preliminary Data). A person's level of hope varies, does not depend on symptom burden, and can be increased through intervention, including brief intervention. Hope interventions have reduced distress in other cancer and non-cancer samples.

**An intervention in primary oncology that incorporates stigma resources could overcome barriers and increase impact.** Hope interventions have not been tested with lung cancer patients. Prior hope-enhancing interventions have used mental health providers, but providers are scarce in areas with high lung cancer incidence (ruralhealthinfo.gov) and not acceptable to many patients. Hope interventions help patients overcome obstacles to goals, which, in lung cancer may include symptom or physical concerns and lung cancer stigma. Therefore, an intervention with symptom and stigma resources delivered in primary oncology is a strong approach. Nurses and other healthcare providers know the symptom and psychosocial concerns patients face, are acceptable to patients (Preliminary Data), and are effective in leading supportive care interventions. Embedding the intervention in oncology reduces utilization barriers and may help the oncology team address symptom or physical obstacles to goals that often are not detected. Finally, addressing stigma as a goal obstacle fills a major intervention gap.

**Preliminary Data**

Study 1: Daily Diary Study of Lung Cancer Patient Quality of Life during Active Treatment (PI: [name]). [name] (PI) designed and conducted a 21-day daily diary study of hope, stigma,

symptoms, and function in 50 lung cancer patients on chemotherapy or chemoradiotherapy. Nearly all patients consented (90%) and completed daily diaries (90%; M daily diaries = 20, SD = 1.3). Patients with higher hope had better function and within-person increases in hope related to function, adjusting for stigma, symptoms, and baseline depression.

Study 2: Cross-Sectional Study of Metastatic NSCLC Patients on Immunotherapy (PI: [name]; NC Lung Cancer Initiative Grant) supports the significance of the intervention in a contemporary treatment era and the intervention design. [name] (PI) designed and conducted a cross-sectional survey purposively sampling 60 stage IV NSCLC patients on immunotherapy in 8 months. This study showed (a) activity and role function concerns remain a top unmet supportive care need (reported by 42% of patients); (b) higher patient hope relates to better role function ( $r = .43$ ), patient goal progress ( $r = .43$ ), and less depression ( $r = -.61$ ) and stigma ( $r = -.40$ ) ( $p$ 's  $<.005$ ); (c) low patient supportive care utilization (<12% had used any service, <2% had seen a mental health provider) and multiple barriers (e.g., time concerns, perceptions about services) to using services.

### 3 OBJECTIVES

#### PRIMARY OBJECTIVES OF PHASE I

1. To refine the Pathways intervention and study protocol based on acceptability feedback from an open pilot study (i.e., fully implement the intervention; Phase I) with patient exit interviews ( $n = 6$ ). We will use feedback on the acceptability of session content, length, and delivery, and review intervention session recordings to refine the intervention. If necessary, we will refine the procedures for enrollment and retention.

#### PRIMARY OBJECTIVES OF PHASE II

1. To determine Pathways intervention feasibility (Phase II;  $n = 55$  Pathways). Feasibility will be defined by enrollment ( $\ge 60\%$  primary feasibility outcome), retention ( $\ge 70\%$ ), adherence ( $\ge 70\%$  of patients completing 3 of 5 sessions), and mean acceptability ratings (scores of  $\ge 7$  out of 10 on intervention relevance, helpfulness, and convenience).
2. To assess preliminary data on intermediate and outcome variables and clinical utility in the single-arm pilot of Pathways (Phase II). We will assess pre (baseline) to post (~8 weeks after baseline) changes in intermediate (e.g., hope) and outcome (primary: activity and role function) variables related to a future efficacy trial. We will also describe the number of referrals to supportive services made based on the Pathways intervention.

### 4 STUDY DESIGN

#### 4.1 OVERALL DESIGN

This is a Stage I, single-site trial to refine and then test the feasibility and acceptability of a novel intervention, Pathways, through a single arm design. Pathways is a 5 session (2 in-person; 3 phone) intervention designed to help patients identify and pursue personal goals and valued activities. To accomplish study objectives, we will 1) fully implement proposed study procedures with 6 patients and conducting patient exit interviews to refine intervention and study procedures (phase I); and 2) conduct a single arm trial of the refined Pathways protocol with 55 patients (phase II). The primary feasibility outcome that will be tested in phase II is enrollment ( $\geq 60\%$ ). Our secondary objective is to gather preliminary patient-reported outcome and clinical utility data (e.g., referrals to supportive services to support a patient goal) on hypothesized intervention mechanisms (hope) and outcomes (e.g., satisfaction with roles and activities) related to a future efficacy trial. Patient-reported data will be collected at baseline and post-intervention (within 14 days of completing the intervention).

#### 4.2 SCIENTIFIC RATIONALE FOR STUDY DESIGN

We considered a control arm to test the feasibility of randomization, but in accordance with the behavioral clinical trial stage model, decided to maintain focus on identifying appropriate intervention materials, eligibility criteria, enrollment/retention strategies, and fidelity monitoring.

#### 4.3 JUSTIFICATION FOR INTERVENTION

The Pathways intervention was developed based on theory, prior hope-enhancing intervention protocols, consultation with content experts, and patient and provider input. Patient feedback informed the number of sessions, frequency, and interventionist.

#### 4.4 END-OF-STUDY DEFINITION

A patient is considered to have completed the study if he or she has completed the baseline assessment, at least 3 intervention sessions, and the post-assessment. The end of the study is defined as completion of the post-assessment.

### 5 STUDY POPULATION

#### 5.1 INCLUSION CRITERIA

In order to be eligible to participate in this study, an individual must meet all of the following criteria:

1. New or recurrent AJCC stage III, IV NSCLC or extensive stage small cell lung cancer
2. 18 years of age or older
3. ECOG performance status 0-2/Karnofsky 60-100;

4. 3-12 weeks into active oncologic treatment (chemotherapy, immunotherapy, chemo-immunotherapy – infusion based systemic treatments).

**Rationale:** We chose 3-12 weeks into active treatment based on patient input to allow time to begin treatment.

## 5.2 EXCLUSION CRITERIA

An individual who meets any of the following criteria will be excluded from participation in this study:

1. Unstable brain metastases (i.e., progressive neurological deficits, inadequately controlled seizures, or requiring escalating steroid doses);
2. Cognitive (i.e., dementia) or psychiatric condition (e.g., psychotic disorder) for which participating would be inappropriate
3. Receiving palliative care or actively receiving psychological services at the cancer center (see Rationale for allowances)
4. Unable to speak and read English.

**Rationale:** Based on preliminary data, most patients will not be using palliative or psychological services. We will consider allowing patients to enroll who are using these services, depending on their focus (e.g., we will allow palliative care for symptom management, counseling for couples' therapy). These cases will be reviewed by the study team. We are unable to include non-English speaking participants in this study because several of the assessment instruments have not been translated or validated in other languages.

## 5.3 SCREEN FAILURES

Screen failures will be defined as patients who consent to participate in this study but are not subsequently assigned to the study intervention due to ineligibility or are assigned to intervention, but do not meet eligibility criteria and are withdrawn by investigators. Patients who do not meet the criteria for participation in this trial because of meeting one or more exclusion criteria that are likely to change over time may be rescreened. Examples include improvement in functional status and a progression of disease or disease recurrence for which a patient will begin treatment for metastatic disease. Rescreened participants will be assigned the same participant number as for the initial screening.

## 5.4 STRATEGIES FOR RECRUITMENT AND RETENTION, PARTICIPANT COMPENSATION

### **Recruitment and Enrollment.**

*Feasibility of Recruitment.* The Markey Cancer Center sees 294 newly diagnosed advanced stage lung cancer patients a year. We estimate 80% will meet performance status and brain

metastases criteria, 85% will receive required active oncologic treatments, and 10% will be excluded for already accessing palliative care or actively receiving psychological services. We estimate 179 patients per year will meet eligibility criteria. With a 50% recruitment rate (based on current estimates during COVID-19), we project recruiting 6 patients in 2 months (Phase I) and 55 patients (Phase II) in 8-9 months.

**Recruitment Strategies.** As in prior work, we will use two primary recruitment strategies: direct patient referral from oncologists and providers at the Markey Cancer Center and review of patient (per report of patients coming to clinic with diagnostic codes for metastatic lung cancer) and provider appointment schedules at the MCC. To facilitate pre-screening for eligibility, we will use the UK CCTS to have an honest broker build a report in Tableau of patients with upcoming Markey Cancer Center appointments and diagnostic codes for metastatic lung cancer. Tableau will link the CCTS Enterprise Data Warehouse data for this information and generate a report that the study team can access via a dashboard in Tableau. Tableau is a secure system that requires SSL and linkblue authentication. Additional eligibility checks may need to occur from within the UKHC medical record. Study personnel will identify upcoming oncology appointments of patients pre-screened for eligibility. Study personnel will then recruit patients in person at clinic appointments or by telephone.

We are requesting a waiver of HIPAA authorization for recruitment purposes. This waiver will allow us to review appointment schedules at the MCC to pre-screen potential patients for eligibility through the electronic health record. Patients will be pre-screened for documentation in their EHR for inclusion and exclusion criteria.

**Inclusion of Women and Minorities.** Men and women of all races and ethnicities who meet the above-described eligibility criteria are eligible to participate in this study. We expect approximately 42% of participants to be women. Translating this to our sample size estimate of 61 (6 pilot; 55 single arm), we plan to enroll at least 25 women. We expect to enroll racially and ethnically diverse patients in proportions that reflect our catchment area: Hispanic/Latino (n = 1), Black or African American (n = 3), American Indian/Alaska Native (n = 1), and Asian (n = 1).

**Retention.** Patients will have up to 12 weeks (from the point of their first session) to complete Pathways. We will use previous retention strategies, including reminding patients of study visits, and offering sessions and assessments when they are in clinic for care. If they are hospitalized and want to participate, the study interventionist will meet them or resume upon discharge.

[figure not shown]
**Participant Compensation.** Patients in both Phase I and Phase II will receive a \$20 gift card for completing the baseline assessment and a \$30 gift card for completing the post-assessment. Patients in Phase I and II will receive an extra \$10 for completing the exit interview. Patients will receive gift cards upon completion of an assessment. Patients will receive the full gift card amount even if they elect to skip measures within an assessment, or, in the case of the exit interview, discontinue the interview.

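### The pre-screening report is limited to metastatic codes although stage III NSCLC is eligible, so stage III patients may be under-represented among those approached

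*Combined protocol and SAP*

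**What the plan says.** Section 5.1, criterion 1, admits "New or recurrent AJCC stage III, IV NSCLC or extensive stage small cell lung cancer". The synopsis agrees, giving the study population as "patients receiving infusion-based systemic therapy for stage III, IV non-small cell lung cancer, extensive stage small cell lung cancer".

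Section 5.4 bases its accrual projection on the same broad group: "The Markey Cancer Center sees 294 newly diagnosed advanced stage lung cancer patients a year". From this it derives 179 eligible patients a year and, at a 50% recruitment rate, 55 Phase II patients in 8-9 months.

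Section 5.4 then names two main recruitment strategies. The first is "direct patient referral from oncologists and providers at the Markey Cancer Center". The second is "review of patient (per report of patients coming to clinic with diagnostic codes for metastatic lung cancer) and provider appointment schedules at the MCC". The Tableau report that supports pre-screening is described in the same terms, as covering "patients with upcoming Markey Cancer Center appointments and diagnostic codes for metastatic lung cancer". The HIPAA waiver paragraph adds: "This waiver will allow us to review appointment schedules at the MCC to pre-screen potential patients for eligibility through the electronic health record".

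Section 9.4.2 and the matching section of the analysis plan define the primary endpoint as patients enrolled over eligible patients approached, and compare it with 60%.

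**The concern.** The eligibility criteria and the accrual base include stage III NSCLC. The one recruitment tool with a stated selection rule does not: both descriptions of it in section 5.4 restrict it to metastatic codes. If staff follow that text, one of the routes to the approached sample omits an eligible group.

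Two things are at stake. The first is representativeness. The endpoint counts only patients who are approached, so an eligible patient whom no route finds leaves both numerator and denominator without trace. The reported proportion would then describe a population with fewer stage III patients than section 5.1 defines. That matters for a pilot meant to inform the eligibility criteria of a later trial; section 9.4.1 plans comparisons to identify the best population for it, though by treatment type and not by stage. The second is accrual, because the 179 a year counts patients whom the report as described would not list.

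**Working it through.** **Inputs from section 5.4.** 294 advanced-stage patients a year; 80% meet the performance status and brain metastasis criteria; 85% receive a qualifying treatment; 10% are excluded for palliative or psychological care; recruitment rate 50%; Phase II target 55.

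**Reproducing the plan's figures.**

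- Eligible per year: 294 × 0.80 × 0.85 × (1 − 0.10) = 179.9. The plan states 179, so the figure reproduces with rounding down.
- Recruited per month: 179 × 0.50 / 12 = 7.46.
- Time to 55: 55 / 7.46 = 7.4 months. The plan states 8-9, so it carries some slack.

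**Inputs not in the documents (assumptions).** Let s be the stage III share of the eligible pool, c the capture of stage III patients relative to other stages, and d the difference in enrollment rate between stage III and the rest. The range used is s = 10-40%, c = 0 to 1, d = 10 or 20 percentage points.

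**Formulas.**

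- Reachable pool = 179 × (1 − s + sc)
- Stage III share of those approached = sc / (1 − s + sc)
- Shift in the enrollment proportion = (s − share approached) × d, with a sign that depends on which stage enrolls more readily

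**Results.**

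| s | c | Reachable pool per year | Stage III share approached | Months to 55 | Shift, d = 10 | Shift, d = 20 |
|---|---|---|---|---|---|---|
| any | 1 | 179 | s | 7.4 | 0 | 0 |
| 10% | 0 | 161 | 0% | 8.2 | 1.0 | 2.0 |
| 20% | 0.5 | 161 | 11% | 8.2 | 0.9 | 1.8 |
| 20% | 0 | 143 | 0% | 9.2 | 2.0 | 4.0 |
| 40% | 0.5 | 143 | 25% | 9.2 | 1.5 | 3.0 |
| 40% | 0 | 107 | 0% | 12.3 | 4.0 | 8.0 |

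The second 20% row, for example: 179 × 0.80 = 143.2; 55 / (143.2 × 0.50 / 12) = 9.2 months; shift (0.20 − 0) × 10 = 2.0 points.

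**When the 8-9 month projection would fail.** Reaching 55 in 9 months needs 55 / 9 = 6.11 a month, or 6.11 × 12 / 0.50 = 147 eligible patients a year. The projection is exceeded only if more than 179 − 147 = 32 eligible patients a year (about 18%) are not found, that is, if s(1 − c) exceeds about 0.18.

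**Scale of the shift.** If 55 enroll at a true rate of 60%, about 55 / 0.60 = 92 are approached, and the standard error of the proportion is √(0.60 × 0.40 / 92) = 5.1 points. A shift of 1-2 points is well inside sampling error; the 8-point extreme is not.

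**The case against.** The strongest reply is that the report is not the only systematic route. The second strategy also covers provider appointment schedules, with no code filter stated, and the waiver paragraph has staff pre-screen those schedules in the health record against the inclusion and exclusion criteria, which admit stage III. This stands. A reader might infer that stage III patients enter mainly by referral, but the documents do not support that.

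A reader might also infer that the samples are in fact skewed, that accrual is in fact lower, or that systematically found stage IV patients are being mixed with hand-picked stage III patients. None of this can be derived. Referral is a main strategy for every stage, nothing shows that referred patients enroll more readily, and no share, yield or rate by stage or route is given.

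The wording may also be left over. The amendment history adds the Tableau report in version 4 and widens eligibility in version 6, and the title and the rescreening example in section 5.3 still speak of metastatic disease. No code list is shown, so the live query may already be broader, and codes may not map exactly to AJCC stage.

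These points limit the concern but do not remove it. The amendment history gives the report's purpose as cutting screening down to patients likely to be eligible, and section 5.4 has staff look up appointments for patients already pre-screened. The more staff rely on the report as intended, the fewer stage III patients the schedules will yield. Nothing in the text ensures equal capture.

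**Conclusion.** The mismatch is real and lies in the current text: section 5.1 and the accrual base include stage III NSCLC, and the report described in section 5.4 does not. Its consequence is a possible, not a demonstrated, under-representation of stage III patients among those approached, and a possible shortfall against the projection.

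The size depends on assumptions that the documents cannot settle. It is zero if referral and schedule review find all stage III patients. At an assumed 20% share and 10-point enrollment difference, the primary proportion moves by 0.9 points (half capture) to 2.0 points (no capture), and 55 patients take 8.2 to 9.2 months against 7.4 on the plan's own inputs. The far end of the assumed range is 8 points and 12.3 months. If enrollment does not differ by stage, the proportion does not move at all, whatever the capture. No sample size, alpha or power figure is affected. This is an inexpensive improvement and not a threat to the primary analysis.

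**What to change.** In section 5.4, align the report filter with inclusion criterion 1: use lung cancer codes that include stage III, with stage confirmed at chart review. Section 5.4 already allows for further eligibility checks in the medical record. If the live query is already broader than described, correct the text to match it.

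On the existing screening form and recruitment log (Appendix L), record stage and identification route (report, schedule review or referral) for every eligible patient approached. The screening fields listed in section 8.1 do not name the route. The form itself is not shown, so it may already hold this. Add to section 9.4 and the analysis plan a descriptive table of enrollment by stage and by route.

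The cost is one query change, at most two fields and one table, plus more charts to screen, including some early-stage patients. That works partly against the report's purpose of narrowing screening. If the change is made during accrual it alters the sampling frame, so its date should be recorded and enrollment shown before and after. If accrual has ended, stage and, where recoverable, route can still be reported.
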